Individual patient response will be defined as an increase of ≥ 1 **ml O₂/kg/min** in VT at 6 months as compared with baseline. Responder rates will be calculated and compared between the treatment and control groups based on both the intent-to-treat population and the per-protocol population using a one-sided binomial comparison with an alpha of 0.025.

The statistical hypothesis to be tested is:

$$H_0: \pi_c \geq \pi_t \quad \text{vs.} \quad H_A: \pi_c < \pi_t$$

Where π_c is the proportion of patients in the control group that have ≥ 1 ml O₂/kg/min improvement in VT at 6 months from baseline and π_t is the proportion of patients in the treatment group that have ≥ 1 ml O₂/kg/min improvement in VT at 6 months from baseline.

2. Primary Safety Analysis

The primary safety analysis shall evaluate the composite event rate of all cause mortality and all cause hospitalization at 12 months. The statistical hypothesis shall be that the proportion of patients in the treatment group where an event occurs by 12 months will be non-inferior to the proportion of patients where an event occurs by the 12 month visit in the control group.

The statistical hypothesis to be tested shall be:

$$H_0: \pi_t > \pi_c + \delta$$

vs.

$$H_1: \pi_t \leq \pi_c + \delta$$

where $\delta=0.125$ (clinically insignificant difference) and π_c is the event rate in the control group and the π_t is the event rate in the treatment group.

The statistical test to be used shall be the Blackwelder non-inferiority test and will be evaluated based on the intent-to-treat patient population and the per protocol patient population. Censoring is expected to be minimal, but in order to determine if there are different patterns of mortality between groups, Kaplan-Meier curves will also be constructed, with Log-rank tests used to determine statistical significance between groups.

The nature, frequency, and seriousness of adverse events between the two groups shall be compared using descriptive summary statistics.

3. **Justification of sample size**

Results of prior studies of CCM and biventricular pacing in which VT has been employed as an endpoint provide estimates for standard deviations of changes and standard deviations of absolute values that may be observed in the present study.

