Baseline NYHA (Site)	0.0779
Baseline NYHA by Optimizer Treatment Interaction	0.2845
Baseline NYHA (Site) (NYHA = 3 or Not)	0.0779
Baseline NYHA by Optimizer Treatment Interaction	0.2845
CHF Etiology	-- ²
CHF Etiology by Optimizer Treatment Interaction	-- ²
Baseline MLWHFQ	0.0445
Baseline MLWHFQ by Optimizer Treatment Interaction	0.2504
BMI	0.7600
BMI by Optimizer Treatment Interaction	0.8891
Race (White)	0.7382
Race by Optimizer Treatment Interaction	0.0506
PTCA or CABG	0.3363
PTCA or CABG by Optimizer Treatment Interaction	0.2056
Baseline Core Lab Exercise Duration	0.0912
Baseline Core Lab Exercise Duration by Optimizer Treatment Interaction	0.3932
Pseudo-Site	0.5091
Pseudo-Site by Optimizer Treatment Interaction	0.7444

¹Covariates with P-values ≤ 0.20 are allowed to enter the competition for the final model (bold face in table). If the interaction is not significant, the P-value reported is for the model with the main effect only.

²The model for CHF etiology did not have a solution so no P-value is reported.

The final model appears was determined by manual backward elimination and the result is presented in the table below. Eight variables were included in the competition for the final model including age, diabetes, baseline NYHA (continuous or categorical), baseline MLWHFQ, race, and race by treatment interaction.

Table 2.2.6 Multivariate Cox Regression Final Model Results for Mortality

Factor	Hazard Ratio	95% CL on HR	P-Value*
Race (White)	0.712	0.535-0.947	0.0197

The treatment term was the last term removed from the model and its P-value at removal was 0.1627. This analysis implies that the only covariate associated with the primary safety composite endpoint of all cause death or hospitalization is race with Caucasians having a lower risk of death or hospitalization than non-Caucasians. Stepwise regression was applied to provide a verification of this models and the same model resulted from that application.

XII. Primary Effectiveness Analysis

For the primary effectiveness analysis, imputation was necessary to obtain study outcomes for patients that did not have an endpoint at 24 weeks. The imputation was done by the methods described in Section IX above. Ten imputations for the ITT patients appear in the tables below. First the means are presented and then the responder analysis (with a responder defined a subject whose AT increased by $\geq 20\%$).

Table XII.1a Mean AT at Study Time Points

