	24 Week Difference From Baseline	-0.27 (2.23) 213 -0.22 (-6.71, 9.34)	-0.13 (2.40) 215 -0.16 (-6.91, 8.94)	0.2711 ²

Table XII.1a Mean AT at Study Time Points (Continued)

Imputation	Time	Control Mean (SD) N Med (Min, Max)	Optimizer Mean (SD) N Med (Min, Max)	P-value
ITT9	Baseline	10.94 (2.28) 213 10.73 (4.10, 17.05)	10.89 (2.30) 215 10.59 (4.10, 16.92)	0.8402 ¹
	24 Week ³	10.72 (2.21) 213 10.72 (4.10, 19.61)	10.80 (2.50) 214 10.40 (4.10, 19.82)	0.7000 ¹
	24 Week Difference From Baseline	-0.22 (2.14) 213 -0.23 (-5.04, 9.34)	-0.08 (2.26) 215 -0.14 (-6.51, 8.94)	0.2645 ²
ITT10	Baseline	10.89 (2.28) 213 10.56 (4.10, 17.05)	10.88 (2.29) 215 10.57 (4.10, 16.92)	0.9462 ¹
	24 Week ³	10.69 (2.33) 213 10.64 (4.10, 19.61)	10.79 (2.45) 214 10.46 (4.10, 19.82)	0.6547 ¹
	24 Week Difference From Baseline	-0.21 (2.34) 213 -0.13 (-8.59, 9.34)	-0.08 (2.25) 215 -0.17 (-6.47, 8.94)	0.2845 ²

¹Two-sided equal variance Student's t-test.

²One-sided equal variance Student's t-test

³One patient in the Optimizer group had a difference imputed but did not have a 24 week AT imputed.

The responder analysis for the 10 imputations appears below.

Table XII.1b Univariate Primary Effectiveness Endpoint Results (≥20% Improvement) for ITT Patients

Population	Control n/N (%)	Optimizer n/N (%)	P-value ¹
ITT1	28/213 (13.15)	37/215 (17.21)	0.1500
ITT2	31/213 (14.55)	37/215 (17.21)	0.2681
ITT3	29/213 (13.62)	38/215 (17.67)	0.1533
ITT4	26/213 (12.21)	39/215 (18.14)	0.0573
ITT5	27/213 (12.68)	40/215 (18.60)	0.0598
ITT6	26/213 (12.21)	36/215 (16.74)	0.1157
ITT7	30/213 (14.08)	36/215 (16.74)	0.2652
ITT8	24/213 (11.27)	39/215 (18.14)	0.0304
ITT9	27/213 (12.68)	40/215 (18.60)	0.0598
ITT10	33/213 (15.49)	38/215 (17.67)	0.3169

¹One-sided Fisher's exact test

Rubin (1987) indicates that the data from multiple imputations can be combined to get an overall test of significance. The method is the basis of Proc MIANALYZE in SAS and is described in the online manual SAS OnlineDoc Version 8, Chapter 10 (Proc MIANALYZE), page 211.

The procedure computes the mean difference across all imputations by the following formula

$$\bar{Q} = \frac{1}{m} \sum_{i=1}^m \hat{Q}_i$$

where Q_i is the difference between the Optimizer proportion and the control proportion for the i th imputation and m is the number of imputations ($M=10$ here)

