The variance is computed as a function of the within imputation variance and the between imputation variance. The estimate of the within imputation variance is given by the following.

$$\bar{U} = \frac{1}{m} \sum_{i=1}^m \hat{U}_i$$

where U_i is the variance of the difference in the i th imputation and is given by the following.

$$U_i = \frac{p_{it}(1-p_{it})}{229} + \frac{p_{ic}(1-p_{ic})}{231}$$

and p_{it} and p_{ic} are the proportions of patient with serious or significant adverse events in the Optimizer and Control groups respectively.

The between imputation variance is obtained by the following formula.

$$B = \frac{1}{m-1} \sum_{i=1}^m (\hat{Q}_i - \bar{Q})^2$$

The total variance is given by the following formula.

$$T = \bar{U} + \left(1 + \frac{1}{m}\right)B$$

and the z-statistic is given by the following.

$$z = \frac{(\bar{Q})}{\sqrt{T}}$$

When these imputations are combined the $z = -0.4839$ with a corresponding P-value of 0.3142.

The mean values for the ITT ten imputations for patients with baseline $EF \geq 25$ are presented below.

Table XII.2a Mean AT at Study Time Points with EF \geq 25 at Baseline

Imputation	Time	Control Mean (SD) N Med (Min, Max)	Optimizer Mean (SD) N Med (Min, Max)	P-value
ITT1	Baseline	11.14 (2.31) 113 10.73 (5.40, 17.05)	10.76 (2.12) 117 10.44 (5.29, 16.08)	0.1909 ¹
	24 Week	10.69 (2.09) 113 10.64 (4.79, 15.50)	10.95 (2.38) 117 10.50 (5.01, 19.82)	0.3763 ¹
	24 Week Difference From Baseline	-0.45 (2.02) 113 -0.33 (-7.29, 5.64)	0.19 (2.45) 117 -0.08 (-4.65, 9.17)	0.0152 ²
ITT2	Baseline	11.17 (2.29) 113 10.76 (5.40, 17.05)	10.74 (2.18) 117 10.44 (5.29, 16.09)	0.1492 ¹
	24 Week	10.73 (2.09) 113 10.64 (6.24, 15.50)	10.83 (2.44) 117 10.39 (5.01, 19.82)	0.7332 ¹
	24 Week Difference From Baseline	-0.44 (2.12) 113 -0.33 (-5.68, 5.64)	0.09 (2.35) 117 -0.14 (-4.65, 8.94)	0.0374 ³
ITT3	Baseline	11.14 (2.31) 113 10.73 (5.40, 17.05)	10.73 (2.09) 117 10.52 (5.29, 16.08)	0.1620 ¹
	24 Week	10.75 (2.12) 113 10.47 (5.99, 15.50)	10.83 (2.37) 117 10.41 (4.97, 19.82)	0.7812 ¹
	24 Week Difference From Baseline	-0.39 (2.12) 113 -0.31 (-6.10, 5.64)	0.10 (2.44) 117 -0.08 (-4.65, 8.94)	0.0533 ³
ITT4	Baseline	11.14 (2.31) 113 10.73 (5.40, 17.05)	10.75 (2.12) 117 10.52 (5.29, 16.08)	0.1864 ¹
	24 Week	10.66 (2.15) 113 10.33 (6.24, 15.79)	10.83 (2.45) 117 10.39 (4.10, 19.82)	0.5746 ¹
	24 Week Difference From Baseline	-0.48 (2.23) 113 -0.31 (-6.03, 6.60)	0.08 (2.33) 117 -0.11 (-4.65, 8.94)	0.0328 ³

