ITT3	12/113 (10.62)	24/117 (20.51)	0.0292
ITT4	10/113 (8.85)	24/117 (20.51)	0.0100
ITT5	11/113 (9.73)	26/117 (22.22)	0.0078
ITT6	10/113 (8.85)	23/117 (19.66)	0.0151
ITT7	13/113 (11.50)	23/117 (19.66)	0.0637
ITT8	10/113 (8.85)	25/117 (21.37)	0.0065
ITT9	11/113 (9.73)	27/117 (23.08)	0.0050
ITT10	14/113 (12.39)	24/117 (20.51)	0.0689

¹One-sided Fisher's exact test

The combination of the 10 ITT imputations in sub-groups by EF, the resulting z = -1.9432 with a corresponding P-value of 0.0260.

The means for the ITT ten imputations with baseline EF \geq 25 and NYHA=3 are presented below.

Table XII.3a Mean AT at Study Time Points with EF \geq 25 and NYHA=3 at Baseline

Imputation	Time	Control Mean (SD) N Med (Min, Max)	Optimizer Mean (SD) N Med (Min, Max)	P-value
ITT1	Baseline	11.19 (2.19) 97 10.73 (7.22, 16.72)	10.72 (2.11) 109 10.44 (5.29, 16.05)	0.1199 ¹
	24 Week	10.70 (2.14) 97 10.47 (4.79, 15.50)	10.98 (2.43) 109 10.57 (5.01, 19.82)	0.3783 ¹
	24 Week Difference From Baseline	-0.49 (1.97) 97 -0.38 (-7.29, 4.62)	0.27 (2.51) 109 -0.02 (-4.65, 9.17)	0.0086²
ITT2	Baseline	11.22 (2.17) 97 10.76 (7.22, 16.72)	10.71 (2.17) 109 10.44 (5.29, 16.09)	0.0916 ¹
	24 Week	10.77 (2.11) 97 10.53 (6.24, 15.50)	10.89 (2.48) 109 10.42 (5.01, 19.82)	0.7109 ¹
	24 Week Difference From Baseline	-0.45 (2.06) 97 -0.38 (-5.68, 4.62)	0.18 (2.38) 109 -0.08 (-4.65, 8.94)	0.0218³
ITT3	Baseline	11.19 (2.19) 97 10.73 (7.22, 16.72)	10.68 (2.07) 109 10.44 (5.29, 16.05)	0.0884 ¹
	24 Week	10.76 (2.18) 97 10.33 (5.99, 15.50)	10.84 (2.41) 109 10.42 (4.97, 19.82)	0.8043 ¹
	24 Week Difference From Baseline	-0.42 (2.11) 97 -0.31 (-6.10, 4.62)	0.16 (2.45) 109 -0.02 (-4.65, 8.94)	0.0336 ³
ITT4	Baseline	11.19 (2.19) 97 10.73 (7.22, 16.72)	10.70 (2.11) 109 10.44 (5.29, 16.05)	0.1067 ¹
	24 Week	10.76 (2.16) 97 10.35 (6.24, 15.79)	10.85 (2.51) 109 10.42 (4.10, 19.82)	0.7673 ¹
	24 Week Difference From Baseline	-0.43 (2.16) 97 -0.27 (-6.03, 6.60)	0.15 (2.38) 109 -0.07 (-4.65, 8.94)	0.0344 ³
ITT5	Baseline	11.22 (2.17) 97 10.76 (7.22, 16.72)	10.69 (2.13) 109 10.39 (5.29, 16.05)	0.0779 ¹
	24 Week	10.77 (2.10) 97 10.35 (6.24, 15.50)	10.93 (2.37) 109 10.62 (5.01, 19.82)	0.5946 ¹
	24 Week Difference From Baseline	-0.45 (1.92) 97 -0.31 (-5.17, 4.62)	0.24 (2.34) 109 -0.02 (-4.65, 8.94)	0.0099²
ITT6	Baseline	11.19 (2.19) 97 10.73 (7.22, 16.72)	10.70 (2.09) 109 10.44 (5.29, 16.05)	0.1075 ¹
	24 Week	10.65 (2.10) 97 10.35 (6.24, 15.50)	10.83 (2.58) 109 10.41 (4.10, 19.82)	0.5872 ⁴

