The analysis of the combined imputations for FASB (EF \geq 25 and NYHA=3) resulted in a z=-2.1549 with corresponding P=0.0156.

These imputation analyses by ITT, FASA, or FASB all resulted in similar outcomes. The whole population does not demonstrate statistical significance at a 0.025. The sub group of patients with baseline EF \geq 25 results in a P-value less than 0.05, but slightly above the 0.025 value and the sub-group with EF \geq 25 and NYHA=3 achieves statistical significance with P<0.025.

XIII. Secondary Effectiveness Analyses

The mean AT and PVO2 at Baseline, 24 weeks and 50 weeks for the CC population are given in the table below.

Table XIII.1a Mean AT and PVO2 at Study Time Points

Variable	Time	Control Mean (SD) N Med (Min, Max)	Optimizer Mean (SD) N Med (Min, Max)	P-value
AT	Baseline	10.97 (2.18) 207 10.73 (5.40, 17.05)	10.95 (2.24) 201 10.60 (5.29, 16.92)	0.9528 ¹
	24 Week	10.96 (2.20) 158 10.83 (6.24, 19.61)	10.87 (2.45) 169 10.49 (5.01, 19.82)	0.7346 ¹
	24 Week Difference From Baseline	-0.14 (2.14) 154 -0.23 (-4.99, 9.34)	-0.14 (2.23) 159 -0.25 (-6.47, 8.94)	0.5040 ³
	50 Week	10.92 (2.49) 148 10.78 (4.10, 20.93)	11.10 (2.56) 163 10.92 (5.40, 21.83)	0.5471 ¹
	50 Week Difference From Baseline	-0.14 (2.64) 146 -0.35 (-6.45, 10.66)	0.01 (2.59) 156 -0.30 (-5.43, 12.25)	0.3158 ³
PVO2	Baseline	14.71 (2.92) 211 15.02 (8.54, 22.61)	14.73 (3.06) 214 14.48 (8.43, 23.02)	0.9245 ¹
	24 Week	14.54 (3.56) 169 14.47 (6.30, 27.95)	14.94 (3.62) 179 14.47 (7.63, 27.49)	0.3008 ¹
	24 Week Difference From Baseline	-0.41 (2.90) 168 -0.50 (-7.68, 11.60)	0.24 (3.16) 179 -0.04 (-8.17, 11.69)	0.0242 ³
	50 Week	14.59 (3.87) 159 14.47 (6.88, 29.75)	14.72 (3.51) 172 14.47 (8.12, 30.67)	0.7394 ¹
	50 Week Difference From Baseline	-0.44 (3.01) 152 -0.58 (-7.80, 12.06)	-0.08 (3.47) 164 -0.21 (-6.87, 17.45)	0.2330 ³

¹Two-sided equal variance Student's t-test.

²Two-sided unequal variance Student's t-test

³One-sided equal variance Student's t-test

The responder analyses for the CC population at 24 and 50 weeks are provided in the table below.

Table XIII.1b Responder Analysis (20% or Greater improvement from Baseline) at Study Time Points

Variable	Time	Control n/N (%)	Optimizer n/N (%)	P-value ¹
AT	24 Week	18/154 (11.69)	28/159 (17.61)	0.0932
	50 Week	21/146 (14.38)	37/156 (23.72)	0.0275
PVO2	24 Week	23/168 (13.69)	31/179 (17.32)	0.2169
	50 Week	24/158 (15.19)	31/172 (18.02)	0.2944

¹One-sided Fisher's exact test

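### Ten imputations are too few to place the EF≥25 result above or below 0.025, and the printed pooled z for that subgroup does not follow from its own responder table.

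*Combined protocol and SAP*

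**What the plan says.** Protocol Section IX.A.1 sets the efficacy comparison: "using a one-sided binomial comparison with an alpha of 0.025". Protocol Section IX.D says that missing data will be imputed, but fixes neither a number of imputations nor a seed.

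Statistical report Section XII states "Ten imputations for the ITT patients appear in the tables below", prints the responder counts for each imputation, and combines them by Rubin's rules: mean difference Q̄, mean within-imputation variance Ū, between-imputation variance B, total T = Ū + (1 + 1/m)B, and z = Q̄/√T. The displayed within-imputation variance uses denominators 229 and 231.

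For EF≥25 in the ITT set it reports "The combination of the 10 ITT imputations in sub-groups by EF, the resulting z = -1.9432 with a corresponding P-value of 0.0260". The corresponding P-values are 0.0269 for FASA and 0.0284 for FASB. The section's conclusion says that this subgroup "results in a P-value less than 0.05, but slightly above the 0.025 value", while EF≥25 with NYHA 3 is called significant and the whole population is not. No seed, Monte Carlo error or reason for m = 10 is given.

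**The concern.** The 0.025 line is what separates the subgroup that the report calls significant from the one that it says narrowly misses. The printed EF≥25 z is 1.960 − 1.943 = 0.017 from that line in absolute value, and the ten single-imputation P-values in Table XII.2b run from 0.0050 to 0.0930. With that much spread between draws, a P-value printed to four decimals from ten draws may not be reproducible to the precision at which it is being read. If it is not, the narrow-miss statement describes neither the patients nor the method reliably.

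**Working it through.** **Inputs (Table XII.2b, ITT, EF≥25).** Control responders of 113: 9, 14, 12, 10, 11, 10, 13, 10, 11, 14 (sum 114). Optimizer responders of 117: 23, 23, 24, 24, 26, 23, 23, 25, 27, 24 (sum 242). m = 10; one-sided critical z = 1.960.

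**Step 1: is the formula the one used?** Applied to Table XII.3b (EF≥25 with NYHA 3, arms 97 and 109), Rubin's rules with the actual arm sizes give Q̄ = 0.1209, T = 0.002854 and z = 2.2624. That is the printed figure, apart from its sign. The FASA version gives 2.2512, also as printed.

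**Step 2: the same formula for EF≥25, ITT.**
- Q̄ = 24.2/117 − 11.4/113 = 0.1060
- Ū = 0.002202; B = 0.000454
- T = 0.002202 + 1.1 × 0.000454 = 0.002701; √T = 0.05197
- z = 0.1060/0.05197 = 2.039, one-sided P = 0.0207

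The printed 1.9432 is not reproduced; the gap is 0.096. The displayed denominators 229 and 231 do not explain it: they match neither the whole-population arms (215 and 213) nor the subgroup arms, and give z = 2.643, P = 0.0041.

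**Step 3: Monte Carlo error of z with m = 10.**
- Formula: √(B/m)/√T = √(0.000454/10)/0.05197 = 0.130
- Simulated fresh sets of ten (Q normal with variance B, Ū fixed): SD 0.155
- Resampling the ten printed imputations: SD 0.163

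The recomputed z is 2.039 − 1.960 = 0.079 above the critical value, about half of one simulated error (0.079/0.155 = 0.51).

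**Step 4: what a new ten-imputation run would show**, simulated around the recomputed values (printed z shown without its sign):

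| Set | Printed z (P) | Recomputed z (P) | Reruns with P < 0.025 |
|---|---|---|---|
| ITT, EF≥25 | 1.9432 (0.0260) | 2.039 (0.0207) | about 70% |
| FASA, EF≥25 | 1.9292 (0.0269) | 2.026 (0.0214) | about 68% |
| FASB, EF≥25 | 1.9045 (0.0284) | 1.953 (0.0254) | about 50% |
| ITT, EF≥25 and NYHA 3 | 2.2624 (0.0118) | 2.262 (0.0118) | about 98% |
| ITT, whole population | 0.4839 (0.3142) | 1.153 (0.124) | about 0% |

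For ITT EF≥25 the 95% range of P over such reruns is about 0.010 to 0.041.

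**Step 5: more imputations, same Q̄, Ū and B.** At m = 200, T = 0.002202 + 1.005 × 0.000454 = 0.002658, so the error is √(0.000454/200)/√0.002658 = 0.029, or about 0.03. For ITT EF≥25 the simulated 95% range of P is about 0.017 to 0.023, with more than 99% of runs below 0.025. For FASB only about 62% of runs at m = 200 fall below 0.025.

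**The case against.** Ten imputations are not an error in themselves. The total variance already contains the finite-m term, and B/m is only 0.0000454/0.002701 = 1.7% of it, so the pooled test is valid; what is lacking is reproducibility. The spread is not hidden either, because all ten sets of counts are printed. The consequence is also limited. The report does not claim pooled EF≥25 as significant, the protocol allots this subgroup no alpha, and the pooled responder is a 20% rise in AT, not the protocol's rise of at least 1 ml O₂/kg/min. All of this stands, and it makes the point a minor one.

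A reader might go further and infer that the random seed put EF≥25 above 0.025, or that the split is a coin toss. The documents do not support that. The ten imputations actually printed for ITT give P = 0.0207, already below the line. The reported position above it comes from an unexplained mismatch between table and text. Near-even odds apply in FASB, or if reruns are centred on the printed z (about 45% below 0.025), but not to the ITT counts.

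Nor does the recomputed 0.0207 make EF≥25 a positive finding: it carries the same Monte Carlo error, and no alpha was reserved for it.

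**Conclusion.** The point holds as a limited one. At m = 10 the error of about 0.13 to 0.16 in z is too large to say on which side of 0.025 the EF≥25 result falls, and the printed ITT value disagrees with its own table by 0.096 in z. About 3 in 10 ten-imputation reruns of the ITT analysis would give P above 0.025, and about half in FASB. The three analysis sets have nearly identical counts and appear to share imputed values, so their agreement is not independent confirmation.

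The whole population stays non-significant on either the printed or the recomputed figure, and ITT EF≥25 with NYHA 3 stays below 0.025 in about 98% of reruns.

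These figures assume that the printed counts are correct and that imputation differences are roughly normal with the variance estimated from ten draws. The rerun shares take the recomputed values as the centre; since that centre is itself uncertain, the true ITT and FASA shares could lie closer to one half.

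**What to change.** 1. Reconcile every pooled z in Section XII with its responder table. Besides EF≥25, the whole-population values and FASB EF≥25 with NYHA 3 (recomputed 2.195, printed 2.1549) do not reproduce. Table XII.7b also prints the FASB10 control count as 30/207 beside 15.94%, which is 33/207.
2. Replace 229 and 231 with the actual arm sizes, and correct the sign of z, which is negative although the difference is defined as Optimizer minus control.
3. Rerun the same imputation program with at least 200 imputations and a recorded seed. Report each pooled difference with its confidence interval and Monte Carlo error.
4. Until then, withdraw the statement that EF≥25 lies slightly above 0.025. Say in the report that FASB may remain too close to call even at m = 200.

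The cost is computer time and an edit to the report; no new data and no change of method are needed.

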All subjects will return to the hospital for follow-up at weeks 4, 12, 24, 36 and 50 following Study Start Date. Each visit shall include an interim medical history, a medication review, and a physical examination. On study Weeks 12, 24 and 50 following Study Start Date, a blinded clinician will perform a site-based NYHA classification and administer a questionnaire for core lab determination of NYHA classification, a 6-minute walk, cardiopulmonary stress test, an echocardiogram and a MLWHFQ will be obtained in addition to device interrogations. 6-minute walk and CPX may be done on the same day a minimum of 3 hours apart. On Weeks 12 and 24, subjects will undergo a Holter monitor examination.

The ICD will be interrogated at 12, 24, 36, and 50-weeks to ascertain proper functioning of the device, in subjects with an ICD. For all subjects, medical regimen for heart failure treatment shall remain fixed unless clinical circumstances dictate otherwise; changes in medical regimen shall be elicited and recorded during the scheduled follow-up visits.

All female subjects shall be asked to notify the Investigators in the event of pregnancy. In addition, women of child bearing potential using medical birth control who receive an OPTIMIZER System implant shall be asked to undergo a pregnancy test at the week 24 and 50 visits. If a patient randomized to device treatment becomes pregnant the device will be turned off. Any study patient who becomes pregnant will continue to be followed for evaluation of safety endpoints.

e. Post Study Follow-Up

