²Pseudo-sites were used in this analysis and are defined in Table 4a.

Table VI.8 Summary of Study Site Comparability¹ for Baseline Medications.

Variable	P-value for Treatment	P-value for Study Site ²	P-value for Site by TRT Interaction
ACEi	0.1089	0.5171	0.0226
ARB	0.4673	0.3345	0.4238
ACEi +/- ARB	0.0518	0.0191	0.0261
B-Blocker	0.5372	0.1887	0.6063
Diuretic	0.4026	0.9576	0.4637
Second Diuretic	0.0122	0.0035	0.0161
Aldosterone Inhibitor	0.1551	0.7007	0.2385
Antiarrhythmic	0.2260	0.3131	0.5036
Hydralazine	0.5334	0.9813	0.7634
Nitrates	0.8873	0.3973	0.6726
Ca Channel Blocker	0.2411	0.3480	0.9998

¹Analysis by logistic regression.

²Pseudo-sites were used in this analysis and are defined in Table 4a.

Table VI.9 Summary of Study Site Comparability¹ for Baseline Cardiopulmonary Exercise

Variable	P-value for Treatment	P-value for Study Site ²	P-value for Site by TRT Interaction
Duration (minutes)	0.4822	0.0022	0.2157
Peak SBP (mmHg)	0.7493	<0.0001	0.5936
Peak HR (bpm)	0.4134	0.0223	0.4897
Peak VO2 (ml/kg/min)	0.9894	0.6534	0.5938
Peak RER	0.7288	0.0020	0.9477
AT (ml/kg/min)	0.9690	0.3116	0.4726

¹Analysis by general linear models analysis of variance with Type III sums of squares.

²Pseudo-sites were used in this analysis and are defined in Table 4a.

Because several baseline variables were significantly different between study sites, study pseudo-site will be used as a possible covariate in multivariate analyses below.

VII. Study Populations

The analysis populations are the intention to treat (ITT) consisting of all subjects randomized. The full analysis set A (FASA), consisting of all randomized patients but excluding patients who never received a study treatment (there were 7 Optimizer and 1 Control patient excluded in this population). The full analysis set B (FASB) consisting of all randomized patients excluding patients who did not receive a study treatment or had no study follow-up (there were 7 Optimizer and 6 Control patients excluded from this population). The population of completed cases (CC) consisting of all patients with a 24 week endpoint. The final population is the per protocol (PP) consisting of all CC patients who did not have a protocol violation that would

substantially affect study outcomes. Imputation by the methods described below is used to provide outcomes for effectiveness for subjects without outcomes in the ITT and FAS populations.

VIII. Comparison of Patient with Missing and Non-Missing Data

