Note that the responder analysis for 24 weeks has a P-value of less than 0.1 and for 50 weeks has a P-value that is near 0.025.

XIV. Additional Analyses

Analyses of additional endpoints are presented below. The means for the quality of life instrument, the MLWHFQ, the NYHA, and the 6 minute walk test (MWT) are provided at 24 and 50 weeks below.

Table XIV.1a Mean AT and PVO2 at Study Time Points

Variable	Time	Control Mean (SD) N Med (Min, Max)	Optimizer Mean (SD) N Med (Min, Max)	P-value
MLWHFQ	Baseline	57.38 (22.62) 213 59.0 (1.0, 102.0)	60.49 (23.00) 215 64.0 (0.0, 100.0)	0.1595 ¹
	24 Week	52.08 (23.84) 184 53.5 (0.0, 105.0)	45.33 (24.43) 196 46.0 (0.0, 97.0)	0.0068 ¹
	24 Week Difference From Baseline	-5.72 (21.03) 184 -6.0 (-74.0, 68.0)	-15.38 (19.55) 196 -12.5 (-81.0, 25.0)	<0.0001 ³
	50 Week	51.10 (23.57) 173 53.0 (1.0, 101.0)	42.75 (25.66) 183 42.0 (0.0, 101.0)	0.0015 ¹
	50 Week Difference From Baseline	-7.32 (20.66) 173 -6.0 (-81.0, 87.0)	-17.60 (22.68) 183 -15.0 (-81.0, 43.0)	<0.0001 ³
NYHA	Baseline	3.13 (0.35) 213 3.0 (2.0, 4.0)	3.09 (0.28) 215 3.0 (3.0, 4.0)	0.1650 ²
	24 Week	2.81 (0.71) 183 3.0 (1.0, 4.0)	2.53 (0.73) 191 3.0 (1.0, 4.0)	0.0002 ²
	24 Week Difference From Baseline	-0.32 (0.73) 183 0.0 (-2.0, 1.0)	-0.54 (0.72) 191 0.0 (-3.0, 1.0)	0.0015 ³
	50 Week	2.67 (0.78) 174 3.0 (1.0, 4.0)	2.48 (0.85) 185 3.0 (1.0, 4.0)	0.0232 ²
	50 Week Difference From Baseline	-0.47 (0.83) 173 0.0 (-3.0, 1.0)	-0.61 (0.86) 185 -1.0 (-3.0, 1.0)	0.0598 ³
6 MWT	Baseline	323.99 (92.44) 212 321.0 (80.0, 600.0)	326.38 (82.10) 215 330.0 (95.0, 525.0)	0.7771 ¹
	24 Week	335.13 (106.99) 173 340.0 (75.0, 730.0)	347.68 (95.47) 190 349.0 (90.0, 585.0)	0.2384 ¹
	24 Week Difference From Baseline	8.61 (85.08) 173 7.0 (-375.0, 457.0)	19.41 (80.62) 190 15.0 (-316.0, 301.0)	0.1079 ³
	50 Week	337.31 (109.49) 162 342.0 (80.0, 823.0)	348.97 (98.34) 181 357.0 (55.0, 615.0)	0.2996 ¹
	50 Week Difference From Baseline	10.51 (87.16) 162 14.0 (-375.0, 365.0)	20.22 (83.14) 181 13.0 (-220.0, 285.0)	0.1449 ³

¹Two-sided equal variance Student's t-test.

²Two-sided unequal variance Student's t-test

³One-sided equal variance Student's t-test

A responder analysis with response being defined as -10 or more points for the MLWHFQ, -1 or more classes for the NYHA, and 40 meters or more for the 6 MWT.

Table XIV.1b Responder Analysis at Study Time Points

Variable	Time	Control n/N (%)	Optimizer n/N (%)	P-value ¹
MLWHFQ ²	24 Week	77/184 (41.85)	110/196 (56.12)	0.0037

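### Secondary outcomes are tested visit by visit in whoever had data, ignoring baseline as a covariate and the week-12 measurements; a baseline-adjusted repeated-measures analysis of data already collected would be more precise and moves some borderline results

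*Combined protocol and SAP*

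**What the plan says.** Section VII of the Statistical Analysis Report defines the completed-case set: "The population of completed cases (CC) consisting of all patients with a 24 week endpoint". Section XIII then states: "The mean AT and PVO2 at Baseline, 24 weeks and 50 weeks for the CC population are given in the table below". Changes from baseline are compared by one-sided two-sample t-tests and responders by one-sided Fisher tests, separately at weeks 24 and 50. Section XIV does the same for MLWHFQ, NYHA and 6MW, and repeats everything in the EF≥25 and the EF≥25 with NYHA 3 subgroups. No comparison is adjusted for the baseline value.

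The protocol schedules an earlier efficacy visit in both arms (Table 1 and section VI.A.3.d): "On study Weeks 12, 24 and 50 following Study Start Date, a blinded clinician will perform a site-based NYHA classification". The 6MW, cardiopulmonary test, echocardiogram and MLWHFQ are listed for the same visits. Sections XIII and XIV show no week-12 result.

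Protocol section IX.D limits the intent-to-treat and worst-case commitments to the primary endpoints. Section IX.A.4 lists the secondary comparisons without naming a test, population or missing-data method.

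**The concern.** The completed-case label suggests one fixed set of patients, but the tables do not use one. In Table XIII.1a, AT has n = 207/201 (Control/Optimizer) at baseline, 158/169 at week 24 and 154/159 for the week-24 change. The MLWHFQ week-24 change has 184/196. The baseline means shown are therefore not those of the patients whose changes are compared.

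Three things follow. First, an available-case test treats those who attended as representative of those who did not, and patients and treating clinicians were unblinded. Second, a patient with week-12 or week-50 data but no week-24 value adds nothing to the week-24 comparison. Third, an unadjusted change score carries any chance baseline difference into the treatment contrast: the arm that starts lower has more room to rise. That matters most in subgroups, where balance is less secure. In EF≥25 with NYHA 3, baseline AT is 11.22 vs 10.63 (printed P = 0.0521).

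**Working it through.** **1. Reproducing a printed result.** Table XIII.1a, peak VO2 change at week 24: Control -0.41 (SD 2.90, n 168), Optimizer 0.24 (SD 3.16, n 179). Difference 0.65, pooled SE 0.326, t = 1.99, one-sided P = 0.0236; rounding of the printed means allows 0.0219 to 0.0253. The printed 0.0242 reproduces.

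**2. Missing change scores.** Missing = 213 (Control) or 215 (Optimizer) minus the n of the change row. For example, the Control 6MW row at week 24 ("335.13 (106.99) 173 340.0 (75.0, 730.0") has 173 patients, as does its change row, so 40 of 213 are missing. P-values are two-sided Fisher.

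| Outcome | Week 24, Control vs Optimizer | P | Week 50, Control vs Optimizer | P |
|---|---|---|---|---|
| AT | 27.7% vs 26.0% | 0.74 | 31.5% vs 27.4% | 0.40 |
| Peak VO2 | 21.1% vs 16.7% | 0.27 | 28.6% vs 23.7% | 0.27 |
| MLWHFQ | 13.6% vs 8.8% | 0.13 | 18.8% vs 14.9% | 0.30 |
| NYHA | 14.1% vs 11.2% | 0.39 | 18.8% vs 14.0% | 0.19 |
| 6MW | 18.8% vs 11.6% | 0.044 | 23.9% vs 15.8% | 0.040 |

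In EF≥25 with NYHA 3 (97 and 109 patients), week 50: 6MW 27/97 vs 14/109 (27.8% vs 12.8%, P = 0.009), peak VO2 28/97 vs 16/109 (28.9% vs 14.7%, P = 0.017), NYHA 20/97 vs 10/109 (20.6% vs 9.2%, P = 0.0285). At week 24 the 6MW gap there is 18.6% vs 11.0% (P = 0.17).

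**3. Precision from baseline adjustment alone.** With s0, s1 and sd the printed SDs at baseline, at follow-up and of the change:

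- r = (s0² + s1² − sd²) / (2·s0·s1)
- variance ratio to the change-score test = s1²(1 − r²) / sd²

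At week 24, r is 0.52-0.66 and the ratios by arm are AT 0.77 and 0.84, peak VO2 0.94 and 0.90, MLWHFQ 0.84 and 0.88, 6MW 0.92 and 0.90. That is 6-23% lower variance.

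**4. Effect on subgroup mean changes.** Adjusted difference = change difference + (1 − β) × baseline gap, with β = r·s1/s0 averaged over arms by n. The SE comes from the residual variances, and P is one-sided normal.

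Worked case, AT week 24, EF≥25 with NYHA 3 (Table XIV.4a):

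- Change difference: 0.10 − (−0.54) = 0.64; printed P = 0.0310.
- β: 0.634 Control, 0.572 Optimizer, average 0.600.
- SE: √(2.71/69 + 4.77/83) = 0.311.
- Using the printed baseline rows, gap = 10.63 − 11.22 = −0.59. Adjusted difference = 0.64 − 0.40 × 0.59 = 0.40, z = 1.30, P = 0.097.
- Using the attenders' implied baseline (week-24 mean minus mean change: 10.93 vs 11.41), gap = −0.48. Adjusted difference = 0.45, z = 1.44, P = 0.075.

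| Row | Printed P | Approximate adjusted P |
|---|---|---|
| Subgroup AT, week 24 | 0.0310 | 0.07-0.10 |
| Subgroup AT, week 50 | 0.0317 | 0.07-0.11 |
| Subgroup peak VO2, week 50 | 0.0174 | 0.03-0.05 |
| All patients, peak VO2, week 24 | 0.0242 | 0.018-0.032 |

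MLWHFQ at week 24 (all patients) goes from −9.7 to about −8.6 points with SE 1.93, so it stays strong.

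**5. What week 12 could add.** No week-12 data are printed. Assuming a week-12 to week-24 correlation of 0.7-0.8, simulation gives a further 1-8% reduction in variance. For 6MW at week 24 with no true effect, if missingness depends on the week-12 value, the t-test is biased by −0.4 to −1.4 m and the repeated-measures model is within 0.2 m of zero. If missingness depends on the unseen week-24 value, both are biased: −1.2 to −3.2 m and −1.1 to −3.8 m. The t-test SE is 8.7 m.

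**The case against.** Several points on the other side stand.

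- Only 6MW missingness is nominally imbalanced in the whole population, without multiplicity adjustment, and 6MW is not significant there anyway (P = 0.1079 and 0.1449).
- AT at week 24 already has imputed means for all randomised patients in section XII, and its missingness is almost equal.
- The closing summary of section XIV argues from responder tables. A model for means alone would leave those untouched, so the fix must cover them.
- Section VIII concedes that the week-24 data are, strictly, not missing at random, and counts 10 Optimizer and 4 Control patients with a death or intervention before week 24. A likelihood model does not cure this and, without a stated strategy, extrapolates outcomes past death.
- The results are already reported, so a new model is post hoc. Table IX.1 also cites a Statistical Analysis Plan that is not recognisable as a separate document in this file, so any planned secondary methods there cannot be checked.

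A reader might infer that the heavier Control loss has inflated the Optimizer results. The documents do not show a direction, and the simulated bias is small against the SE. A reader might also infer that a repeated-measures model would analyse all 428 patients, or the same patients at each visit. It would not: 6 Control and 7 Optimizer patients had no follow-up (section X), and those observed still differ by visit.

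**Conclusion.** The point holds as one of efficiency and baseline imbalance first, and missing data second. The tests are unadjusted and available-case, and they leave scheduled week-12 data unused. Control missingness is higher in 10 of 10 whole-population rows, but clearly so only for 6MW; the widest gaps are at week 50 in EF≥25 with NYHA 3.

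It would be too strong to say that the secondary conclusions fall. MLWHFQ is robust. The adjusted P-values concern mean changes, not the responder rates on which the summary relies. Of the subgroup rows recomputed, only peak VO2 at week 50 crosses 0.025; the two AT rows were already above it and move past 0.05. Whole-population peak VO2 at week 24 straddles 0.025.

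These figures rest on printed SDs from slightly different patients at each time, a normal approximation, and either of two baseline gaps. Patient-level data would settle them.

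**What to change.** - For MLWHFQ, 6MW, peak VO2 and AT, report a likelihood-based repeated-measures model on randomised patients with at least one post-baseline value: weeks 12, 24 and 50, baseline covariate, treatment by visit, unstructured covariance. Use an ordinal equivalent for NYHA. Give week-24 and week-50 contrasts with 95% CIs. Present AT at week 24 beside the imputed means of section XII.
- Reanalyse the responder tables (XIII.1b and XIV.1b to XIV.5b) with a baseline-adjusted binary model, or derive responders after multiple imputation.
- State how death, LVAD, transplant and corrective surgery enter each analysis, and add a not-missing-at-random sensitivity analysis.
- Keep the present tables as sensitivity analyses, relabelled available-case, and label the new analyses post hoc.
- Reconcile the peak VO2 week-50 row of Table XIII.1a. Its printed inputs (152/164) give P = 0.16, not 0.2330, and the responder row uses 158/172.

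The cost is a few model runs and some report text, with no new patients or visits. The model assumes data missing at random, which is weaker than what the current tests need.
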